#### 6 RATIONALE

Nu-3 is a thymidine-based therapeutic compound indicated for the reduction of pathogenic bacteria associated with chronic diabetic foot ulcers. The animal data from both rodent and swine models of wound injury and its anti-fungal as well as anti-bacterial activity suggest that treatment with Nu-3 may reduce and potentially eliminate pathogenic bacteria in patients

pathogens' - capable of 'escaping' the biocidal action of antibiotics and mutually representing new paradigms in pathogenesis, transmission and resistance.

<sup>2 In recent years, the Infectious Diseases Society of America has highlighted a faction of antibiotic-resistant bacteria (Enterococcus faecium, Staphylococcus aureus, Klebsiella pneumoniae, Acinetobacter baumannii, Pseudomonas aeruginosa and Enterobacter spp.) — acronymically dubbed 'the ESKAPE

with chronic diabetic foot ulcers. The topical route of administration will be the appropriate method of delivery for humans. The low order of toxicity in rodents suggests that Nu-3 has a very low risk of toxicity to humans at the proposed doses. The doses selected for evaluation are within the FDA guidelines of the recommended safety margin of one tenth of the NOAEL.

Prior to determining the efficacy of Nu-3 in patients, safety of Nu-3 related to skin irritation was established in male and female healthy volunteers in a Human Repeat Insult Patch Test. Briefly, 20 microliters of positive control (0.1% sodium lauryl sulfate), test product (2% Nu-3 in 0.85% saline), or negative control (0.9% saline) was randomly applied using occlusive patches to either abraded or non-abraded (intact) skin for 20 consecutive days on at least 30 subjects. A total of 35 subjects completed the study and were scored on all six sites. There was a difference among products for both abraded and intact skin sites. The conclusion from the study with regards to irritation was as follows:

Abraded Skin: Positive Control > 2% Nu-3 > Negative Saline control

Intact Skin: Positive Control > 2% Nu-3 = Negative Saline Control

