### 7.1 **Primary Objective**

The primary objective of this study is

• To assess the safety and tolerability of a twice daily, 7-day repeat topical doses of Nu-3 in adult male and female patients with chronically infected diabetic ulcer.

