### **Diabetic Foot Ulcer Wound Infection Score**

Parameter	Wound Infection Score			
	0	1	2	3
Purulent discharge	Absent			Present
Nonpurulant drainage (serious, sanguinous)	Absent	Mild		
Erythema	None	Mild pink, barely perceptible	Moderate pale red, defined edges	Severe red to dark red
Induration	None	Mild	Moderate	Severe
Tenderness (sign)	None	Mild	Moderate	Severe
Pain (symptoms)	None	Mild	Moderate	Severe
Local Warmth (relative to uninfected contralateral foot)	Same	Mildly increased	Moderately increased	Severely increased

Photo Documentation and Calculation of the Ulcer Area and Depth using the Aranz Medical SilhouetteTM as described in Appendix A

A past medical/surgical history will be recorded for any conditions or treatments that are, in the opinion of the investigator, relevant to the current diagnosis. The previous condition will be recorded as a diagnosis rather than a previous symptom. The time of the previous diagnosis relative to the current admission will be provided (i.e., "6 months ago") to the best of the patient's knowledge. If the diagnosis was more than two years ago, then it can be recorded as "more than two years ago".

Prior medications will be recorded. Prior medications include medications that the patient is currently taken or has taken within the past fourteen days.

Physical examinations are performed at screening by the investigator or designee. The screening examinations will include general appearance, height, weight, skin, neck, eyes, ears, nose, throat, heart, lungs, abdomen, cervical and axillary lymph nodes, extremities, and nervous system. Height is measured in stocking or bare feet, and recorded in centimeters (cm). Weight is recorded in kilograms (kg).

Results of these investigations/assessments and baseline measurements obtained from the local laboratory will be reviewed by the Investigator prior to the start of the treatment. Patients who do not meet study entry criteria will be promptly notified and excluded from further participation in the study. Patients who continue to meet entry criteria will be enrolled in the study and assigned a patient number by the database. The patient can be randomized at any time following the screening.

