## **8. EFFICACY ANALYSIS**

### **8.1 Definition of Efficacy Endpoints**

All efficacy endpoints will be summarized by visit and evaluated statistically at the end of the MAD portion of the study. Efficacy endpoints include:

- The proportion of subjects with a normal culture
- The change from baseline in the DUSS score
- The change from baseline in the DFI score
- The absence of each of the following as reported by the investigator on the CRF:
  - Purulent discharge
  - Nonpurulent drainage
  - Erythema
  - Induration
  - Tenderness
  - PainLocal warmth (no change)
- Data captured on the total wound size for each subject using the Aranz Medical Silhouette™ System:
  - Wound area (cm^2)

- Percentage of area reduction
- Perimeter (mm)
- Maximum depth (mm)
- Mean depth (mm)
- Volume (cm^3)
- Length (mm)
- Width (mm)

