## **8.2 Analysis of Efficacy Endpoints**

For each dose group, the proportion of subjects with a normal culture at the end of the MAD portion of the study will be compared to the proportion of subjects with a normal culture at the end of the MAD portion of the study for the combined placebo group using a Fisher's exact test. A subject with a normal culture at this time will be considered a success. Any subject with a missing value at the end of the MAD portion of the study will not be included in the analysis. A p-value less than 0.05 will be considered statistically significant and a p-value less than 0.0167, employing a Bonferroni correction for multiple comparisons, will be considered highly conclusive.

For continuous efficacy endpoints, data will be summarized descriptively at and a comparison using the Wilcoxon Rank Sum test between each of dose groups and the combined placebo group will be performed at each visit. For these endpoints, no imputation for missing values will be performed.

For categorical endpoints, a Fisher's exact test will be performed in a similar manner. Subjects missing a value for a secondary endpoint will be considered a failure (counted in the denominator) for that endpoint.

For all tests, a p-value less than 0.05 will be considered statistically significant and a p-value less than 0.0167, employing a Bonferroni correction for multiple comparisons, will be considered highly conclusive. Analysis for each secondary endpoint will be performed on the ITT population and the PP population.

Ulcer measurements and percentage of area reduction will be summarized descriptively by visit and statistical testing using a Wilcoxon Rank Sum test between each dose group and the combined placebo group. For all tests, a p-value less than 0.05 will be considered statistically significant. Analysis for each additional endpoint will be performed on the ITT population and the PP population.

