### **9.1 Adverse Events**

All AE summaries will be restricted to Treatment-Emergent Adverse Events (TEAE), which are

defined as those AEs that occurred after dosing and those pre-existing AEs that worsened during the study. Verbatim terms on case report forms will be mapped to preferred terms and system organ classes using the MedDRA dictionary (version 14.1).

Each AE summary will be displayed by dose group. Summaries that are displayed by system organ class and preferred terms will be ordered by descending order of incidence of system organ class and preferred term within each system organ class. Summaries of the following types will be presented:

- Subject incidence of TEAEs and total number of unique TEAEs by MedDRA system organ class and preferred term.
- Subject incidence of TEAEs by MedDRA system organ class, preferred term, and highest severity. At each level of subject summarization, a subject is classified according to the highest severity if the subject reported one or more events. An event with missing severity will not be imputed.
- Subject incidence of TEAEs by MedDRA system organ class, preferred term, and closest relationship to study drug (Not Related, Unlikely, Possibly, Probable, Definite). At each level of subject summarization, a subject is classified according to the closest relationship if the subject reported one or more events. AEs with a missing relationship will be considered definite related for this summary.
- Subject incidence of serious TEAEs and total number of unique serious TEAEs by MedDRA system organ class and preferred term.

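### Five wound signs graded 0 to 3 are tested singly only as absent or not absent, so worsening of a sign already present does not show at sign level, and no DFI analysis is planned on the Safety population

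*SAP*

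**What the plan says.** **Signs taken singly.** SAP 8.1 makes an efficacy endpoint of "The absence of each of the following as reported by the investigator on the CRF" and names seven signs. SAP 8.2 adds: "For categorical endpoints, a Fisher's exact test will be performed in a similar manner". Each dose group is compared with combined placebo, a missing value counts as a failure, and the populations are ITT and PP.

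**The scale.** The Protocol's Diabetic Foot Ulcer Wound Infection Score grades erythema, induration, tenderness, pain and local warmth from 0 to 3; grade 2 erythema, for example, is "Moderate pale red, defined edges". Purulent discharge is scored only 0 or 3, and nonpurulent drainage shows only 0 or 1. The Protocol's Schedule of Events places the score at Visits 1, 4 and 5 (screening, Day 9, Day 15).

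**The total.** The same list in SAP 8.1 contains "The change from baseline in the DFI score". For continuous endpoints SAP 8.2 says "a comparison using the Wilcoxon Rank Sum test between each of dose groups and the combined placebo group will be performed at each visit".

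**Safety.** SAP 9.1 provides "Subject incidence of TEAEs by MedDRA system organ class, preferred term, and highest severity", and a further table by closest relationship to study drug. Pre-existing events that worsen count as TEAEs. In SAP Appendix A the DFI tables (14.2.3.1 to 14.2.3.4) are ITT or PP only. Listing 16.2.10 gives DFI scores, and the visual ulcer examination appears only as Listing 16.2.15.

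**Purpose.** Protocol 7.1 states the primary objective: "To assess the safety and tolerability of a twice daily, 7-day repeat topical doses of Nu-3". Protocol 6 reports from the patch test: "Abraded Skin: Positive Control > 2% Nu-3 > Negative Saline control".

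**The concern.** The five graded signs describe infection, but they are also what local irritation by a topical product looks like. The Protocol's own patch test ranked 2% Nu-3 above saline for irritation on abraded skin, 2% is the top dose in the SAP, and the product goes onto open ulcers. A structured grade of each sign is planned for every subject before dosing, at the end of treatment and at follow-up. At sign level the SAP uses only one cut on that scale, zero against anything else. Unchanged, worse and missing all fall into the same cell.

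The SAP treats heart rate and blood pressure differently: 9.2 counts subjects in the Safety population whose values rise by set amounts. The local signs, which bear more directly on the tolerability of a topical drug, get no equivalent count. What is at stake is whether a dose-related rise in one local sign would be visible in a planned table, or would have to be found in a listing.

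**Working it through.** **Plan's own figure.** SAP 8.2 states no power or sample size. Its one reproducible number is the Bonferroni threshold: 0.05 / 3 = 0.0167, which agrees. Nothing below depends on it.

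**Inputs.** Allocation is 4:1 in cohorts of 10, so 8 active and 2 placebo per cohort. SAP 3 has three cohorts: pooled placebo 3 × 2 = 6. Protocol 8.3 has five cohorts: 5 × 2 = 10. Tests are two-sided (SAP 4).

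**Scenario (assumed).** One sign is mild (1) in everyone before dosing. At Day 9, k of 8 Nu-3 subjects are severe (3). All other Nu-3 subjects, all placebo subjects and all other signs are unchanged.

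*Step 1: the sign-level test.* Nobody is at zero, so the comparison is 0/8 against 0/6 (or 0/10). Fisher p = 1.00 for every k from 0 to 8.

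*Step 2: graded change on the same data.* Change is +2 in k subjects and 0 in the rest. Taking the total as the sum of the items, its change is identical here, so the Wilcoxon columns are also what the SAP's total-score test would give.

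| k of 8 worse | Absent/not absent, Fisher | 8 v 6, exact | 8 v 6, Wilcoxon (asymptotic) | 8 v 10, exact | 8 v 10, Wilcoxon (asymptotic) |
|---|---|---|---|---|---|
| 3 | 1.00 | 0.209 | 0.124 | 0.069 | 0.046 |
| 4 | 1.00 | 0.085 | 0.058 | 0.023 | 0.016 |
| 5 | 1.00 | 0.031 | 0.025 | 0.0065 | 0.0051 |
| 6 | 1.00 | 0.0097 | 0.0086 | 0.0015 | 0.0013 |

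When nothing else moves, the planned total-score test therefore does see the worsening.

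*Step 3: when something else moves.* Suppose a Nu-3 subject has erythema 1 to 3 (+2) and purulent discharge 3 to 0 (−3). The total changes by 2 − 3 = −1, which reads as improvement. If all 8 Nu-3 subjects did this and 6 placebo subjects with the same baseline did not change, the exact p on the total would be 1/C(14,8) = 1/3003 = 0.0003 in favour of Nu-3. The purulent-discharge item would also favour Nu-3 (8/8 against 0/6). The erythema item would show 0/8 against 0/6, p = 1. No planned DFI test would show that erythema became severe in every treated subject.

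*Step 4: what a worsening count would show.* Clopper-Pearson 95% intervals for a rise of 2 grades or more, with k = 3:
- Nu-3: 3/8 = 37.5%, 8.5% to 75.5%.
- Placebo, three cohorts: 0/6, upper limit 1 − 0.025^(1/6) = 45.9%.
- Placebo, five cohorts: 0/10, upper limit 1 − 0.025^(1/10) = 30.8%.

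**Reach.** The loss of grades affects five of seven signs. The two drainage items have two levels each, so absent/not absent loses nothing for them.

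**The case against.** The strongest answer is that the plan already looks at graded harm in two places.

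First, the total DFI change uses the grades, is tested two-sided and rises when a sign worsens; step 2 shows it responding where the sign-level test gives p = 1. A reader might infer from the sign-level endpoint that the graded data can show benefit but not harm. The documents do not support that.

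Second, a reader might infer that tolerability has no scored analysis. That is not so either. SAP 9.1 tabulates TEAEs on the Safety population by highest severity and by relationship. Protocol 12.7 has local reactions such as pain, edema, rash and cellulitis recorded as AEs at every visit. Protocol 13.4 grades AEs by CTCAE, and Protocol 8.10.5 feeds related Grade 2 or higher events into the escalation decision.

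It can also be said that this is an unpowered pilot, that the counts above are invented, and that the Appendix B table shells are not available, so Tables 14.2.3.3 and 14.2.3.4 may show counts by grade.

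Most of this stands, but it leaves a gap. The total nets signs against each other (step 3). A worse ulcer sign becomes a TEAE only if the investigator reports it; nothing in the Protocol makes a rise in a DFI item an AE, and a redder infected ulcer can be read as disease. Counts by grade at each visit, if the shells contain them, would still not show within-subject change and would still be on ITT and PP.

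The drainage items may also look contradictory, since a wound going from purulent to nonpurulent drainage could fail the second item. That assumes a purulent wound scores zero for nonpurulent drainage, which the Protocol does not say. Such a wound would succeed on the first item and its total would fall by 2. Merging the two items is a preference, not a correction.

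**Conclusion.** The point holds in a limited form. For five of seven signs the sign-level test cannot register worsening of a sign already present: p = 1.00 even if all 8 treated subjects go from mild to severe. The total score and the TEAE tables cover part of the gap. They do not cover irritation offset by reduced discharge, or local worsening that is not reported as an AE. No by-sign worsening summary and no Safety-population DFI analysis is described, although safety and tolerability is the primary objective.

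The conclusion rests on the SAP text as written, on the total being the sum of the item scores, and on invented counts that only illustrate the mechanism. Under the SAP's three cohorts each comparison is 8 v 6; the 8 v 10 figures apply only to the Protocol's five cohorts. At either size the intervals are wide, so the gain is a visible count for each dose, not a test. The change is worth making because it is cheap and serves the primary objective. The planned analyses remain valid for what they measure.

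**What to change.** 1. Keep the total DFI change analysis and the TEAE tables as they are.
2. In SAP 8.1 and 8.2, for erythema, induration, tenderness, pain and local warmth, summarise the change from the pre-dose grade on the 0 to 3 scale, in place of or beside absent/not absent. State that the pre-dose value is the screening score, the only DFI rating scheduled before dosing.
3. Add to SAP section 9 and Appendix A a Safety-population table by dose group and pooled placebo. For each of the five signs it gives the number of subjects whose grade rose by 1 or more, and by 2 or more, at Day 9 and at Day 15, with exact 95% confidence intervals, presented descriptively. Show the number with both values, so that missing is not counted as worse or as unchanged.

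The cost is some SAP wording and one more table. No new data are needed, because the score is already taken at Visits 1, 4 and 5. The drawback is a set of wide by-sign intervals that must be read as description.

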## **8.2 Analysis of Efficacy Endpoints**

For each dose group, the proportion of subjects with a normal culture at the end of the MAD portion of the study will be compared to the proportion of subjects with a normal culture at the end of the MAD portion of the study for the combined placebo group using a Fisher's exact test. A subject with a normal culture at this time will be considered a success. Any subject with a missing value at the end of the MAD portion of the study will not be included in the analysis. A p-value less than 0.05 will be considered statistically significant and a p-value less than 0.0167, employing a Bonferroni correction for multiple comparisons, will be considered highly conclusive.

For continuous efficacy endpoints, data will be summarized descriptively at and a comparison using the Wilcoxon Rank Sum test between each of dose groups and the combined placebo group will be performed at each visit. For these endpoints, no imputation for missing values will be performed.

For categorical endpoints, a Fisher's exact test will be performed in a similar manner. Subjects missing a value for a secondary endpoint will be considered a failure (counted in the denominator) for that endpoint.

For all tests, a p-value less than 0.05 will be considered statistically significant and a p-value less than 0.0167, employing a Bonferroni correction for multiple comparisons, will be considered highly conclusive. Analysis for each secondary endpoint will be performed on the ITT population and the PP population.

Ulcer measurements and percentage of area reduction will be summarized descriptively by visit and statistical testing using a Wilcoxon Rank Sum test between each dose group and the combined placebo group. For all tests, a p-value less than 0.05 will be considered statistically significant. Analysis for each additional endpoint will be performed on the ITT population and the PP population.

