### 7 OBJECTIVE

The objective of this study is to evaluate Nu-3 for safety, tolerability, and microbiological response to bacteria in patients with chronic diabetic foot ulcer, but excluding any ulcer caused by an underlying DUSS Probing to Bone = "Yes".

This study will specifically examine the ability of different doses of Nu-3 to eliminate pathogenic bacteria in patients with chronic diabetic foot ulcers. Dose and regimen information will be obtained for future clinical studies of Nu-3.

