### 12.4 Visit 3 (Day 2 [24 h $\pm$ 2 h.]) MAD Treatment

Patients will return after the Single Ascending Dose Treatment. Patient disease assessments will be performed as specified in the schedule of events table.

- Vital signs (blood pressure, heart rate, temperature) will be examined within 10 minutes prior to the start of treatment
- Baseline Patient Disease Assessment: Visual examination of chronic ulcer, score target ulcer using DUSS Scoring System, Swab wound to culture for microbiological examination
- Photo Documentation and Calculation of the Ulcer Area and Depth using the Aranz Medical SilhouetteTM System

The Principal Investigator will visually exam the chronic ulcer to determine if a patient is eligible to continue in the study. Eligible patients will be provided with his/her designated test product kit and instructed to apply the product twice daily for one (1) week (7 days). Test product application will be demonstrated, and patient instruction sheet reviewed, using the assigned test product. The patients will be observed applying the first dose in the clinic to ensure compliance (administering Test Product to the infected diabetic foot ulcer and surrounding intact skin at a dose of 1 to 3 drops from a dropper bottle per 1 cm^2 of ulcer area, left open to air for 5 minutes and then dressed using Owens gauge, Kerlex and tape.). The patient will be scheduled for the next follow-up visit, with a reminder to bring the test article kit to the visit.

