## 9.2 Vital Signs

Vital sign assessments will be analyzed by dose group at baseline and each scheduled post-baseline visit. Mean observed measurements and mean changes from baseline will be summarized. Baseline is defined as the last non-missing value obtained prior to receiving study drug.

An outlier analysis will be performed to provide counts and percentage of subjects above or below certain cutoffs for specific vital sign parameters. The following cutoffs will be used in the outlier analysis for the vital signs data:

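### SAP 8.2 counts any normal end-of-MAD culture as a success whatever the pre-dose culture, so its rates are not elimination rates; and the rule for a missing culture is not settled

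*SAP*

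**What the plan says.** The objective in Protocol 7 is to "examine the ability of different doses of Nu-3 to eliminate pathogenic bacteria in patients with chronic diabetic foot ulcers". Protocol 16.5 also speaks of elimination; Protocol 14.1 speaks of reduction.

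SAP 8.1 lists the endpoint as "The proportion of subjects with a normal culture". SAP 8.2 compares that proportion at the end of MAD between each dose group and pooled placebo by Fisher's exact test, and adds: "A subject with a normal culture at this time will be considered a success". The pre-dose culture plays no part in this definition. For DUSS and DFI scores, by contrast, SAP 8.1 uses change from baseline.

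The SAP text supplied defines baseline in one place, SAP 9.2, for vital signs: "Baseline is defined as the last non-missing value obtained prior to receiving study drug". Protocol 12.2, 12.3 and 12.4 all put a swab under a baseline heading. The one in 12.4 is taken on Day 2, after the first dose: "Baseline Patient Disease Assessment: Visual examination of chronic ulcer, score target ulcer using DUSS Scoring System, Swab wound to culture for microbiological examination".

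Three rules could govern a missing culture:

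- SAP 8.2, culture paragraph: "Any subject with a missing value at the end of the MAD portion of the study will not be included in the analysis". The result feeds Table 14.2.1.1, labelled ITT, and SAP 5.1 defines ITT as everyone randomised.
- SAP 8.2, categorical endpoints: "Subjects missing a value for a secondary endpoint will be considered a failure (counted in the denominator) for that endpoint".
- Protocol synopsis, Analysis Populations: LOCF for efficacy variables. Protocol Section 16 does not repeat this.

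**The concern.** Elimination is a before-and-after idea: a pathogen was present and is gone. A rule that looks only at the last culture gives the same credit to a subject who cleared a pathogen and to one who had none to clear. Protocol 9.1.1 and 9.1.2 do not close this gap, because neither asks for a positive culture. Subjects normal from the start raise the success rate in both arms and shrink the difference between them. A reader choosing a dose range, which is a stated secondary objective, would see a placebo rate that is partly not response at all.

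On missing data, the arms are so small that one subject matters. If the rule is still open when the codes are broken, the choice can determine the result.

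**Working it through.** **Inputs.** SAP 3 gives three cohorts of 10 at 4:1, so 8 on each dose and 3 × 2 = 6 pooled placebo. The current protocol (8.3, 8.4) gives five cohorts, so 8 v 5 × 2 = 10. Tests are two-sided at 0.05 (SAP 4). The one derived figure in the SAP paragraph reproduces: 0.05/3 = 0.0167. The documents give no culture rates and no dropout rate, so the rates below are assumptions.

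**Dilution.** Let b be the share normal before dosing, assumed to stay normal, and e the elimination rate among the rest. The reported success rate is b + (1 − b)e. With b = 0.20:

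- Nu-3, e = 0.60: 0.20 + 0.80 × 0.60 = 0.68
- Placebo, e = 0.10: 0.20 + 0.80 × 0.10 = 0.28

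A 50-point contrast becomes 40 points. At b = 0 the two definitions coincide; for example, power at 8 v 6 and 80% elimination is 69.6% either way.

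**Validity.** With equal 10% elimination in both arms and b of 20% to 40%, the test as written rejects in 1.2% to 2.0% of trials at 8 v 6, and in 2.3% to 2.4% at 8 v 10. The chance of a pre-dose split that would itself look like an effect (at least 5 of 8 normal on Nu-3 and 0 of 6 on placebo) is 0.02%, 0.27% and 0.8% at b = 10%, 20% and 40%.

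**Power, as written v restricted to subjects non-normal before dosing.** Exact enumeration, b = 20%, placebo elimination 10%. The restricted test is averaged over the binomial number of non-normal subjects in each arm.

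| Nu-3 elimination | 8 v 6 | 8 v 10 |
|---|---|---|
| 80% | 41.7% v 51.8% | 56.9% v 72.7% |
| 60% | 19.2% v 19.3% | 27.2% v 39.2% |
| 50% | 12.3% v 9.7% | 17.7% v 24.5% |
| 30% | 4.0% v 1.2% | 6.4% v 5.5% |

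At 80% elimination and 8 v 6, over b = 10% to 40%, power as written falls from 54.3% to 21.7%, and restricted from 60.1% to 34.5%.

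**One missing culture.** Suppose 6 of 7 observed Nu-3 cultures and 1 of 6 placebo cultures are normal, with one Nu-3 culture missing. The two-sided Fisher p sums the tables no more likely than the one observed:

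- Excluded, 6/7 v 1/6: (42 + 1 + 7)/1716 = 0.029
- Counted as failure, 6/8 v 1/6: (168 + 8 + 8 + 168)/3432 = 0.103

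A missing placebo culture can act the other way: 5/8 v 0/5 gives p = 0.075, and 5/8 v 0/6 gives p = 0.031. At 8 v 10, 6/7 v 2/10 gives 0.015 and 6/8 v 2/10 gives 0.054.

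Given exactly one missing Nu-3 culture, with b = 20% and elimination of 50% to 80%, the two rules disagree on significance with probability 5% to 22% at 8 v 6 and 8% to 28% at 8 v 10.

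**The case against.** The best defence is that randomisation protects the comparison. Subjects normal before dosing fall in both arms by chance, so the test remains a fair test of treatment. That stands: a reader might infer that the p-value is invalid or inflated, and the rejection rates above show that it is not.

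The share normal before dosing may also be small. The trial is meant for infected ulcers, and exclusion 4 in Protocol 9.1.2 bars antibiotics in the preceding seven days. The share could be near 0%, and the assumption that such subjects stay normal is untested. This limits the size of the problem; nothing in eligibility rules it out. By-visit summaries (SAP 8.1) and Listing 16.2.8 would show pre-dose status, but display does not change the definition that is tested.

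Two stronger readings do not hold. A reader might infer that the SAP nowhere defines a normal culture. The table and listing shells (SAP Appendices B and C) are not in the supplied text, so a definition there cannot be excluded. A reader might also infer that SAP 8.2 plainly contradicts itself on missing data. The missing-as-failure sentence is limited to secondary endpoints. SAP 2 and the protocol synopsis put microbiological response under secondary objectives, but Protocol 14.1 calls it the primary efficacy endpoint. On that reading, 8.2 sets different rules for different tiers. Exclusion would still sit badly with an ITT label and with LOCF in the synopsis.

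**Conclusion.** The point holds in a limited form. The tested endpoint is culture status at one time, not conversion, so the reported proportions cannot be read as elimination rates. The cost to the comparison is dilution: from 50 points to 40 if 20% are normal before dosing and remain so, and nothing if none are. The rule for a missing culture is unsettled across the documents, and at these arm sizes one subject can move the result across 0.05 in either direction.

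The weight is minor to should-fix. This is a non-safety endpoint in a pilot without a sample size calculation, and all the culture rates used here are assumptions. The main reason to change is that the result would then answer the question in Protocol 7; more power follows only when the effect is large relative to the arm sizes.

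**What to change.** 1. In SAP 8.2, define culture baseline as the last swab before the Day 1 dose, in line with SAP 9.2. If the table shells do not already define a normal culture, do so, stating whether growth of normal flora counts.
2. Report and test conversion from non-normal to normal at the end of MAD among subjects non-normal at baseline. List baseline-normal subjects separately and keep the all-subject proportion alongside.
3. Before unblinding, choose one missing-culture rule that fits the ITT label, report the alternative (observed-case or missing-as-failure) as a sensitivity analysis, and reconcile the LOCF sentence in the protocol synopsis.

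This needs SAP wording, one extra table and one correction to the synopsis. The pre-dose swabs are already scheduled (Protocol 2, 12.2, 12.3).

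The costs should be stated openly. The denominator is smaller. At a 20% baseline-normal share, restriction lowers power at 8 v 6 for 50% elimination (12.3% to 9.7%), and at 8 v 10 for 30% elimination (6.4% to 5.5%). Missing-as-failure is also not free: at 80% elimination and the same share, with one Nu-3 culture missing, power is 44.4% under exclusion and 22.3% under missing-as-failure at 8 v 6, and 60.5% against 32.3% at 8 v 10. Which rule to adopt is a trade-off; having a single rule in advance is not.
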